**“The effects of Neurodevelopmental Therapy on Feeding and Swallowing
Activities in Children with Cerebral Palsy”**

NCT04403113

15.02.2018

STUDY PROTOCOL

Scientific background:	
The trunk plays an important role in the organization of postural control and balance reactions because it holds the centre of all body mass and holds therefore, the centre of gravity. The trunk also provides stable attachment points to those muscles that control the head and neck regions. Neck and trunk stabilization exercises were the basis of static and dynamic balance abilities, and that increased neck and trunk stability might have had a positive effect thereon. To achieve the alignment of the head with the trunk, the pelvis must be stabilized. This has important consequences for the entire process of swallowing. If the head is not stable, then the fine movements of the jaw and tongue needed for feeding will be impaired. With feeding and oral-motor interventions and structured neck and trunk stabilization exercises, these parameters are positively affected.

Objectives:	
Our study is planned to investigate the effects of neck and trunk stabilization exercises, which are structured from the principles of Neurodevelopmental Therapy Method-Bobath (NDT-B), added to feeding and oral motor intervention strategies (OMIS) and nutrition-related caregiver training (NRCT) on feeding and swallowing activities in children with cerebral palsy (CP).

Design, Arm description:	
-Feeding and oral motor intervention strategies+structured neck and trunk stabilization exercises+caregiver training related to feeding (Study Group).
 
-Feeding and oral motor intervention strategies+caregiver training related to feeding (Control Group).
 
Intensive structured neck and trunk stabilization exercises based on Neurodevelopmental therapy method-Bobath concept principles. These exercises were performed for 6 weeks, 2 days a week, 45 minutes for a total of 12 sessions. Feeding and oral motor intervention strategies program were performed for 6 weeks, 2 days a week, 45 minutes for a total of 12 sessions. In caregiver training related to feeding; a) positioning and feeding technique during feeding, b) ensuring safety for aspiration, c)

	using suitable containers and ingredients, d) adjusting (adapting) food consistency properly, e) preparing small amounts of high-calorie, balanced diet and f) reducing food spillage while feeding and how to ensure efficacy for shortening the feeding time, g) providing appropriate postural and physical support for self-feeding. All of these activities were continued for 6 weeks with a home program.
Sponsor:	Marmara University, Istanbul, Turkey
Measured Parameters:	
 -Gross Motor Functions, -The Eating and Drinking Ability, -The Mini-Manual Ability, -Trunk Functionally, -Oral-Motor Function in Children with Dysphagia, -The Quality of Life for Children with CP, - Fiberoptic Endoscopic Evaluation of Swallowing (FEES).
Study Center:	Marmara University Pendik Education And Research Hospital, Istanbul, Turkey

All procedures performed in studies involving human participants were in accordance with the ethical standards of the institutional and/or national research committee and with the 1964 Helsinki declaration and its later amendments or comparable ethical standards. Ethical approval was obtained from the Marmara University Faculty of Medicine Clinical Research Ethics Committee protocol code 09.2018.278.

"The effects of Neurodevelopmental Therapy on Feeding and Swallowing Activities in Children with Cerebral Palsy" NCT04403113

03.12.2019

Statistical Analysis Plan

Descriptive statistics for continuous variables are expressed as mean, standard deviation values (Height, weight, body mass index (BMI), gender, etc); it is expressed as number (n) and percentage (%) for categorical variables.

In calculations, statistical significance level (α) was taken as 5% and values with P < 0.05 expressed statistical significance. "Statistical Package for Social Sciences" (SPSS 16) statistical program was used in the analysis of the data.

In statistical analysis, the suitability of all the data to normal distribution was analyzed with "One-Sample Kolmogorov-Smirnov Test" and non-parametric tests were used since the variables were not normally distributed. Chi-square test was used in binary analyzes (CP subtypes). Mann-Whitney U was used for comparing the group's data. In inter-group comparisons, the Mann-Whitney U test (pre-treatment TIS parameters and post-treatment TIS parameters; PedsQL) were analyzed. Wilcoxon test was used for intra-group comparisons.

Spearman Correlation test analysis method was used in non-parametric correlation analysis (TIS subscales and SOMA's cups, puree, semi-solids, solids and crackers after treatment).

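### Neither document names a primary outcome or controls multiplicity, so the 5% level does not bound the error of a treatment-effect conclusion

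*SAP*

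**What the plan says.** The SAP sets the significance level at 5% and states that "values with P < 0.05 expressed statistical significance". No other decision rule appears.

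For comparisons between the arms it has two sentences. The first is general: "Mann-Whitney U was used for comparing the group's data". The second names some variables: "pre-treatment TIS parameters and post-treatment TIS parameters; PedsQL". Neither says how many tests there will be or whether the named variables are the full set. Wilcoxon tests are planned within each group, and Spearman correlations are planned for "TIS subscales and SOMA's cups, puree, semi-solids, solids and crackers after treatment".

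The protocol's Measured Parameters entry is an unranked list of seven: gross motor function, then "The Eating and Drinking Ability, -The Mini-Manual Ability, -Trunk Functionally", then oral-motor function, quality of life and FEES. Its Objectives entry states the target only as a domain, feeding and swallowing activities. Neither document has a sample size calculation from which a primary outcome could be inferred.

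**The concern.** A 5% level describes the risk of a false claim only when it is clear which test the claim rests on. Here nothing says which between-group result decides the objective. Several results could be significant by chance, and the one that is emphasised can be picked once the data are known. A reader of the report could not tell a planned finding from a selected one.

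The objective makes the gap more specific. Trunk function (TIS) and quality of life (PedsQL) are the only outcomes the SAP names for a between-group test, and neither document presents them as feeding or swallowing measures. SOMA appears only in the correlation analysis. The comparison that would answer the trial's question is therefore not identified.

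The Wilcoxon and Spearman tests do not fill the gap. Both arms receive oral-motor intervention and caregiver training, so either arm may improve without any difference between arms. TIS and SOMA may also be correlated without any treatment effect.

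**Working it through.** **Inputs from the documents**
- Per-test level 0.05, applied to every test (SAP).
- Two arms, so the multiplicity comes from outcomes (Protocol, Design and arm description).
- Seven measured parameters (Protocol, Measured Parameters).
- TIS and PedsQL named for between-group tests; SOMA listed with five categories: cups, puree, semi-solids, solids, crackers (SAP).

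**Assumptions, because the documents do not give these values**
- Number of between-group tests, *k*:
  - *k* = 2: post-treatment TIS and PedsQL, one test each. Pre-treatment TIS is a baseline comparison and is not counted.
  - *k* = 3: only the parameters closest to the objective (eating and drinking ability, oral-motor function, FEES).
  - *k* = 7: one test per measured parameter.
  - *k* = 11: as for seven, with SOMA taken to be the oral-motor measure and tested as five categories (7 − 1 + 5).
- Common correlation *r* between the test statistics, from 0 to 0.8.
- All null hypotheses true, and each test of size exactly 5%.
- Wilcoxon and Spearman tests are not counted, because they do not compare the arms.

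**The plan's own figure.** For one test, 1 − 0.95 = 5%. The stated level is exact for *k* = 1 only.

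**Independent tests.** The chance of at least one false positive is 1 − 0.95^*k*:
- 1 − 0.95² = 9.75%
- 1 − 0.95³ = 14.3%
- 1 − 0.95⁷ = 30.2%
- 1 − 0.95¹¹ = 43.1%

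**Correlated tests.** For *k* equally correlated two-sided z-tests, with φ and Φ the standard normal density and distribution function, the chance is

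1 − ∫ φ(u) · [Φ((1.96 − √r·u)/√(1−r)) − Φ((−1.96 − √r·u)/√(1−r))]^*k* du.

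Numerical integration gives:

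| *k* | r = 0 | r = 0.3 | r = 0.5 | r = 0.7 | r = 0.8 |
|---|---|---|---|---|---|
| 2 | 9.75% | 9.5% | 9.1% | 8.4% | 7.8% |
| 3 | 14.3% | 13.6% | 12.5% | 10.9% | 9.8% |
| 7 | 30.2% | 27.2% | 23.0% | 17.8% | 14.9% |
| 11 | 43.1% | 37.5% | 30.4% | 22.3% | 18.0% |

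Simulation with 400,000 draws agrees for *k* = 2, 7 and 11 to within simulation error. Every cell exceeds 5%.

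**Price of a correction.** The first and strictest Holm threshold is 0.05/*k*. For an outcome assumed to have 80% power at two-sided 5%, the mean of its z-statistic is 1.960 + 0.842 = 2.802, and power at that step is Φ(2.802 − z), where z is the two-sided critical value:
- *k* = 2: threshold 0.025, z = 2.241, power 71%
- *k* = 7: threshold 0.0071, z = 2.690, power 54%
- *k* = 11: threshold 0.0045, z = 2.838, power 49%

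**The case against.** The strongest reply concerns which tests count.

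- **Scope of the family.** The objective is limited to feeding and swallowing, so a chance result on gross motor function or quality of life would not answer it. Only about three parameters are candidates, which gives 9.8% to 14.3%. This is a fair narrower reading. It roughly doubles or triples the stated error, and the SAP does not adopt it: the outcomes it names for between-group tests are outside that set.
- **Counting.** The SAP speaks of TIS parameters in the plural, yet TIS is counted once above while SOMA is split into five. This is correct. Two is therefore a minimum count, eleven is not a maximum, and the figures are scenarios and not limits set by the documents.
- **The 43% figure.** It requires independence among five categories of one instrument in the same children, which is implausible. At correlation 0.7 to 0.8 the same count gives 18% to 22%, and that is the more credible part of the range.
- **Exceptions to the direction.** Perfectly correlated tests would keep the error at 5%. Exact Mann-Whitney tests in very small samples are conservative: with an illustrative 4 children per arm the attainable size is 2/70 = 2.9%, and two tests at correlation 0.8 give about 4.6%. The documents state no sample size. The exception is narrow, because three such tests at the same correlation already give 5.8%.
- **Exploratory intent.** Labelling the analyses exploratory and reporting estimates with intervals would also prevent overclaiming. Neither document does so, and the unqualified significance rule points the other way.

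These points change the size of the inflation. They do not supply a primary outcome or an error-control rule.

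**Conclusion.** The concern holds. As written, the plan lets any between-group P below 0.05 stand as evidence of a treatment effect, with no designated outcome and no adjustment. The direction requires only two or more imperfectly correlated tests, each of size close to 5%. The size depends on the assumed count and correlation: 7.8% to 43% over all the readings above, 9.8% to 14.3% for a family restricted to the objective, and 15% to 30% for one test per measured parameter. The finding concerns these two documents; a primary outcome stated elsewhere would need to be carried into them. Each single test keeps its nominal level, so this is a defect that should be corrected and not one that invalidates every analysis.

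**What to change.** **Preferred.** Name one feeding or swallowing outcome as primary, chosen from the objective and without knowledge of the results. Test it between groups at two-sided 5% and base the conclusion on it. Apply Holm at 5% to the remaining between-group outcomes, and claim significance for them only if the primary is significant. The overall error then stays at 5%, and the primary loses no power.

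**Fallback.** The SAP is written in the past tense and reports that the variables were not normally distributed, so a choice blind to the results may no longer be possible. In that case list every between-group comparison, count each separately tested subscale as its own test, and apply Holm to the whole list. Holm is valid whatever the correlation between the tests.

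**In both cases.** Rest treatment-effect claims on between-group comparisons only, and report the TIS–SOMA correlations as exploratory.

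**Cost.** Only SAP wording changes, and no new data are needed. Under the preferred route only the secondary outcomes face stricter thresholds. Under the fallback all outcomes do: from an assumed 80%, power at the first Holm step falls to 71%, 54% or 49% for two, seven or eleven tests, and later steps are less strict. Separately tested TIS subscales would lengthen the list and lower the first threshold further.

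### The SAP names no between-group comparison of change, or of outcome adjusted for baseline; the only pre-post test is within each group

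*SAP*

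**What the plan says.** The SAP names five procedures. Kolmogorov-Smirnov is for normality. Chi-square is for CP subtypes ("Chi-square test was used in binary analyzes (CP subtypes"). Spearman correlation is for scores after treatment ("TIS subscales and SOMA's cups, puree, semi-solids, solids and crackers after treatment"). The other two bear on the treatment effect:

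- Between groups, there is a general statement, "Mann-Whitney U was used for comparing the group's data", which gives neither variable nor time point. A specific one follows: "In inter-group comparisons, the Mann-Whitney U test (pre-treatment TIS parameters and post-treatment TIS parameters; PedsQL) were analyzed". TIS is listed before and after treatment as separate variables, and PedsQL has no time point.
- Within groups: "Wilcoxon test was used for intra-group comparisons". That this compares pre with post is an inference from the wording, though a natural one.

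The protocol (Objectives) asks what the neck and trunk exercises contribute on top of the feeding strategies and caregiver training. Under Design, Arm description, the comparator is itself treated: "Feeding and oral motor intervention strategies+caregiver training related to feeding (Control Group". Neither document says how children were allocated to the two groups.

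**The concern.** The objective is a between-group question about children measured before and after treatment. As named, the tests split that question in two. The between-group tests look at one time point at a time, and the test that seems to use both time points never compares the groups. Testing pre-treatment TIS between groups does not remove any imbalance from the post-treatment comparison.

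Three things are at stake:

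- With random allocation, precision is given up and a chance baseline imbalance goes uncorrected.
- If allocation was not random, a systematic baseline difference would carry straight into the post-only comparison.
- Both arms receive active treatment, so both may improve. A Wilcoxon test that is significant in one arm only could then be misread as a treatment effect. This is a risk; the SAP does not say it intends that reading.

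**Working it through.** The documents contain no sample size, power, effect size, SD or correlation, so there is no figure to reproduce. The only stated input is the 5% significance level (SAP), with sidedness not given; two-sided is assumed. Everything else below is assumed: 10 to 30 children per arm, a 0.8 SD effect where power is shown, and pre-post correlation ρ over a range.

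**Step 1: precision by formula.** Relative to a post-only comparison (variance 1), a change-score comparison has variance 2(1 − ρ) and a baseline-adjusted comparison 1 − ρ². For a 0.8 SD difference and 80% power, the normal approximation gives n per arm = 2(1.96 + 0.84)² × variance / 0.8², rounded up.

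| ρ | Change: variance | Change: n | Adjusted: variance | Adjusted: n |
|---|---|---|---|---|
| 0.3 | 1.40 | 35 | 0.91 | 23 |
| 0.5 | 1.00 | 25 | 0.75 | 19 |
| 0.7 | 0.60 | 15 | 0.51 | 13 |
| 0.8 | 0.40 | 10 | 0.36 | 9 |

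Post-only needs 25 per arm throughout.

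**Step 2: power by simulation.** Mann-Whitney on the post score (tie- and continuity-corrected) against rank ANCOVA, 0.8 SD effect, 15 per arm, 20,000 replicates:

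| ρ | Normal: post-only | Normal: rank ANCOVA | 4 categories: post-only | 4 categories: rank ANCOVA |
|---|---|---|---|---|
| 0 | 0.528 | 0.533 | – | – |
| 0.3 | 0.521 | 0.563 | 0.486 | 0.513 |
| 0.5 | 0.521 | 0.635 | 0.486 | 0.575 |
| 0.7 | 0.526 | 0.774 | 0.490 | 0.690 |
| 0.8 | 0.527 | 0.886 | 0.487 | 0.776 |

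For the 4-category scores, ρ is the correlation of the underlying continuous scores.

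**Step 3: no effect, random allocation.** With normal scores, post-only rejects in 4.0% to 5.0% of trials and rank ANCOVA in 4.9% to 5.1%. The chance of a baseline mean difference above 0.5 SD is 2(1 − Φ(0.5/√(2/n))). For n = 15, √(2/15) = 0.365 and 0.5/0.365 = 1.37, which gives 0.171. At 10, 15, 20 and 30 per arm it is 26%, 17%, 11% and 5%. In those trials, with ρ = 0.7, post-only rejects in 12%, 16%, 21% and 29%, and rank ANCOVA in about 5%. In the remaining trials post-only rejects in only about 2% to 3.5%, which is why its overall rate stays near 5%.

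**Step 4: no effect, systematic 0.5 SD baseline gap, ρ = 0.7.** If the gap shrinks to 0.7 × 0.5 = 0.35 SD after treatment, as ANCOVA assumes, post-only rejects in 10% to 24% of trials (10 to 30 per arm) and rank ANCOVA in about 5%. If the full gap persists, the figures are 16% to 45% and 8% to 13%. Adjustment then reduces the bias without removing it.

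**Step 5: within-group tests.** If both arms truly improve equally and each Wilcoxon test has power p, exactly one is significant with probability 2p(1 − p). For a 0.5 SD improvement and 15 per arm, p is 0.416 at ρ = 0.5 and 0.619 at ρ = 0.7. The formula gives 2 × 0.416 × 0.584 = 0.49 and 2 × 0.619 × 0.381 = 0.47, and simulation gave 0.487 and 0.466. This is near the 50% maximum. Across 10 to 30 per arm and improvements of 0.3 to 0.7 SD, it ranges from 0.006 to 0.501.

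**The case against.** The general Mann-Whitney sentence could cover change scores, so what is certain is under-specification and not a post-only plan. On that reading, and with the assumptions of Step 2, Mann-Whitney on change has power 0.74 against 0.77 for rank ANCOVA at ρ = 0.7, and 0.89 for both at 0.8, so the largest gains nearly vanish. This stands as a caution about size. But the SAP explicitly lists post-treatment TIS and never mentions change. A change score also does no better than post-only at ρ = 0.5 (0.52, against 0.63 for rank ANCOVA) and is worse below that.

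Under random allocation the matter is one of efficiency. That is correct. The conditional rejection rates in Step 3 describe a subset of trials, offset by the rest.

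The systematic-gap figures arise from unstated allocation, which is a separate problem that adjustment does not cure. That is also correct, and the case for the change does not need them.

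The Wilcoxon misreading is hypothetical, and the 47% to 49% figure lies near the maximum. Both points stand; the full range is given above.

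The claim that adjustment costs no power depends on the continuity correction, which the SAP does not mention. Without it, at zero correlation, post-only has 0.54 against 0.53 at 15 per arm and 0.39 against 0.37 at 10. The loss is 1 to 2 percentage points in the least favourable case.

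**Conclusion.** The concern holds. Neither document names a between-group comparison of change or of outcome adjusted for baseline. The post-only test is not invalid if children were randomised; it is less precise and leaves chance imbalance uncorrected. The gain from adjustment depends on a pre-post correlation that the documents do not give: nil at 0, small at 0.3, about 11 percentage points of power at 0.5 and about 25 at 0.7 (15 per arm, 0.8 SD effect, normal scores), and somewhat less with coarse ordinal scores. This should be changed, because it uses data already collected and costs almost nothing. Confidence in the reading of the text is high; the sizes are illustrations under stated assumptions.

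**What to change.** For TIS and every other outcome recorded both before and after treatment, name rank ANCOVA as the between-group test: regress the ranked post score on group and the ranked pre score. It keeps to the SAP's non-parametric approach. State which of the seven measures under Measured Parameters in the protocol this covers, since time points and scale types are not given there. The calculations above cover continuous and ordinal scores, not binary outcomes. A proportional-odds model with baseline is an option where category counts allow.

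Show pre-treatment values by group descriptively. Label the within-group Wilcoxon results as descriptive and state that they are not the treatment comparison. The SAP is written in the past tense; if results already exist, report the adjusted analysis as added later.

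The cost is SAP wording, one regression per outcome and one degree of freedom, with at most a 1 to 2 point loss of power if pre and post scores are uncorrelated. The change does not repair a systematic baseline difference if allocation was not random.

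### The within-arm Wilcoxon tests cannot show a treatment effect. The SAP should label them descriptive and rest efficacy on a between-arm comparison that explicitly includes SOMA and FEES.

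*SAP*

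**What the plan says.** The protocol's design entry describes two concurrent arms. Both receive the feeding and oral-motor strategies and the caregiver training, and only the study group adds the neck and trunk exercises. The Objectives entry frames the question as the effect of those exercises "added to feeding and oral motor intervention strategies (OMIS) and nutrition-related caregiver training (NRCT) on feeding and swallowing activities". The exercises and the oral-motor programme each run for 6 weeks, and a home programme is also described: "All of these activities were continued for 6 weeks with a home program". No untreated arm, waiting list or run-in is described.

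The SAP sets one significance rule for all tests (P below 0.05). For comparisons between arms it says in general that "Mann-Whitney U was used for comparing the group's data", and then names pre- and post-treatment TIS parameters and PedsQL. For comparisons within an arm it says only that "Wilcoxon test was used for intra-group comparisons". SOMA appears only in a post-treatment correlation with TIS. FEES, a measured parameter in the protocol, is not named in the SAP.

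**The concern.** A Wilcoxon test within one arm has zero pre-post change as its null hypothesis. In growing children that null can be false without any treatment effect: through development, through familiarity with the assessment, or through regression to the mean if children entered when feeding was at its worst. A small P value then shows that scores moved, not why.

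Two misreadings become available. If both arms reach significance, the report may say that both programmes work, although nothing in this design isolates the effect of the shared care. If only the study arm does, the report may credit the exercises, although no test has compared the arms.

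The risk is greatest for feeding and swallowing, the outcomes in the trial's title. The SAP does not specifically commit to a between-arm test of SOMA or FEES, so within-arm P values could end up carrying that conclusion.

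**Working it through.** **Reading the plan.**
1. The arms differ only in the added exercises (protocol, design entry). The concurrent contrast therefore addresses the exercises and nothing else.
2. The within-arm test makes no use of the other arm, so it does not use that contrast.
3. The SAP neither limits the within-arm tests to description nor ranks them below the between-arm tests.
4. The between-arm tests named specifically cover TIS and PedsQL. SOMA and FEES rely on the general sentence.

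**Illustrating the size.** The plan has no figure to reproduce: it gives no sample size, SD or expected change. Everything below is assumed except the 5% level, which is the SAP's (taken as two-sided).

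*Shared drift.* Change scores are drawn from N(d, 1) in both arms with the same d and no treatment effect; d is in SDs of change. There are 4,000 simulated trials per setting. Entries are the share with one given arm's Wilcoxon P below 0.05.

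| n per arm | d = 0 | d = 0.3 | d = 0.5 | d = 0.8 |
|---|---|---|---|---|
| 10 | 4.3% | 13.0% | 27.8% | 59.8% |
| 15 | 4.9% | 18.5% | 41.1% | 80.4% |
| 20 | 4.1% | 24.9% | 55.0% | 91.3% |
| 30 | 5.1% | 34.0% | 73.5% | 98.7% |

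A Mann-Whitney test on change between arms is significant in 3.8% to 5.3% of trials across all 16 settings.

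*Two arms read side by side.* For independent arms, each significant with probability p:
- At least one significant: 1 − (1 − p)². With p = 0.411 (n = 15, d = 0.5), 1 − 0.589² = 0.653; simulated 0.661.
- Exactly one significant: 2p(1 − p) = 2 × 0.411 × 0.589 = 0.484; simulated 0.484.
- With no drift and p = 0.05, at least one: 1 − 0.95² = 0.0975.

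So at n = 15 and d = 0.5, nearly half of trials with identical arms would show one arm significant and the other not.

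*Regression to the mean alone.* Baseline and follow-up have variance 1 and correlation r, and children enter only if baseline is below c. The expected change is (1 − r) × φ(c)/Φ(c). For c = 0, φ/Φ = 0.399/0.5 = 0.798; for c = −0.5, it is 0.352/0.309 = 1.14. Simulated with n = 15 per arm, 2,000 trials per setting:

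| r | c | Expected change | Wilcoxon, one arm | Mann-Whitney on change |
|---|---|---|---|---|
| 0.6 | 0 | 0.4 × 0.798 = 0.32 | 27.5% | 4.5% |
| 0.6 | −0.5 | 0.4 × 1.14 = 0.46 | 50.5% | 4.6% |
| 0.8 | 0 | 0.2 × 0.798 = 0.16 | 15.1% | 5.4% |
| 0.8 | −0.5 | 0.2 × 1.14 = 0.23 | 27.1% | 4.8% |

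**The case against.** The strongest reply is that the harm is predicted rather than documented. The SAP gives the Wilcoxon test one sentence, attaches no conclusion to it, and plans between-arm tests as well. That is correct. The point is therefore about a gap in the SAP's wording, not about a claim already made.

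Four stronger readings are tempting, and the documents do not support them.

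- **The missing untreated arm is a design flaw.** It is not. An add-on question calls for the same background care in both arms. An untreated arm would not repair a within-arm test either.
- **The background already treats the oral-motor programme as proven.** The sentence reads "With feeding and oral-motor interventions and structured neck and trunk stabilization exercises, these parameters are positively affected". It describes that programme combined with the exercises and does not isolate the programme. It need not be deleted.
- **The percentages are false-positive rates for this trial.** If drift is real, rejecting zero change is a correct rejection; the figures are the chance of detecting an assumed drift. The error would lie in attributing that drift to treatment. Drift, sample size, selection at entry and a 6-week gap between assessments are all assumptions.
- **SOMA and FEES are excluded from between-arm testing.** The general Mann-Whitney sentence may cover them. The SAP just does not say so.

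One further limit stands. The figure near 5% belongs to a Mann-Whitney test on change scores, which the SAP does not mention; it refers to pre- and post-treatment TIS values.

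**Conclusion.** The point holds as a gap in what the SAP lets the trial conclude. Within-arm Wilcoxon P values cannot support an efficacy claim for either arm's programme, and comparing significance across arms does not test the added exercises. This follows from the structure of the test and depends on no assumed number.

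Its size in this trial is unknown. Under the assumed drifts of 0.3 to 0.8 SD and 10 to 30 children per arm, one arm's Wilcoxon test is significant in 13% to 99% of trials without any treatment effect; under the regression-to-the-mean settings the range is 15% to 51%. The between-arm figure near 5% assumes that both arms share the same drift and selection. The documents do not state how children were allocated, so that protection cannot be confirmed. The between-arm test is still the only one with a concurrent comparator.

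The trial's ability to address its add-on question is not in dispute here.

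**What to change.** Replace the SAP's Wilcoxon sentence with:

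> Within-group change is summarised descriptively (median change, IQR) and within-group P values are not used as evidence of treatment effect. Efficacy conclusions concern only the added neck and trunk exercises and rest on the between-group Mann-Whitney comparison of pre-to-post change, applied to the feeding and swallowing outcomes (SOMA, FEES) as well as TIS and PedsQL. No efficacy conclusion is drawn for OMIS or caregiver training, which both arms received.

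This presumes that each named outcome was scored before and after treatment, which the SAP makes explicit only for TIS. It should confirm this for the others.

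The cost is SAP wording and a few additional between-group tests on measures already listed. No new arm or visit is needed, and the protocol background can stay as it is. The downside is that the report can no longer claim that both groups improved significantly as a finding of efficacy.
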